### **Expectedness**

Expectedness will be classified by the Sponsor on the basis of the RSI of study drug, included in the ivermectin SmPC.

### **Assessment of cases with multiple SAEs**

Whenever possible, SAEs (including laboratory abnormalities that constitute SAEs) should be described using a diagnosis, rather than individual underlying signs and symptoms. When a clear diagnosis cannot be identified or when more diagnoses occur at the same

time, each sign/symptom or diagnosis should be reported in a single SAE form and the main SAE should be listed as first. Each SAE should be independently assessed for causality, seriousness, severity, onset date and outcome by Investigators and for expectedness by the Sponsor.

## ***Reporting***

### **AE**

AEs notification will be carried out completing the relative page on the study eCRF.

### **SAE**

To ensure patient safety, every SAE, regardless of suspected causality, occurring from the acquisition of the informed consent until the date of last visit must be immediately reported to Sponsor and always within 24 hours of learning of its occurrence.

The investigator will notify the Study safety desk all SAEs occurring during the treatment period.

To notify the Sponsor, the identified SAEs should be recorded and described on the appropriate SAE form of the eCRF, which should be dated and signed electronically. By clicking on a specific link in the form, an automatic email will be sent to Study Safety Desk and to all Investigators with EDC system access.

In case the EDC system is malfunctioning, the SAE should be notified by completing an editable pdf SAE form provided during the site activation and sending it by email or fax within 24 hours of the initial observation of the event to the Study safety desk:

Laboratory of Methodology for Clinical Research

Istituto di Ricerche Farmacologiche Mario Negri IRCCS

Study Safety Desk

email: [[contact]](mailto:[contact])

Fax: [name]

Once EDC system functionality is restored, all the cases reported through the pdf SAE form must be entered in the electronic SAE form of the EDC system.

Any new or additional information regarding the SAE must be reported as follow-up to the original episode within 24 hours of the investigator receiving the follow-up information. Once

a SAE is detected, it should be followed until its resolution or until it is judged to be permanent. Follow-up information is sent to the same contact(s) to whom the original SAE report form was sent, using a new SAE report form stating that this is a follow-up to the previously reported SAE.

The repetition of the same SAE after its resolution should be reported as a second separate event.

### **Suspected Unexpected Serious Adverse Reactions (SUSARs)**

The management of suspected unexpected serious adverse reactions (SUSARs) will be done according to the guideline 2011/C 172/01 "Detailed guidance on the collection, verification and presentation of adverse event/reaction reports arising from clinical trials on medicinal products for human use ('CT-3')" based on Article 18 of directive 2001/20/EC of the European Parliament and of the Council of 4 April 2001 on the approximation of the laws, regulations and administrative provisions of the Member States relating to the implementation of good clinical practice in the conduct of clinical trials on medicinal products for human use.

According to the CT-3, the SUSARs will be notified via EudraVigilance to Competent Authorities:

- within 7 days if the SUSAR results in death or is life-threatening
- within 15 days if the SUSAR is not fatal and not life-threatening

For this purpose, the Sponsor is registered to EudraVigilance as Sponsor of not-for-profit clinical trials.

All SUSARs will be notified to the Coordinating Ethics Committee and to the trial Investigators.

### ***Deaths***

All deaths that occur from date of acquisition of informed consent to the end of the safety follow-up period (25 days after the last study drug administration), must be reported as follows:

- Death which is clearly the result of COVID- 19 disease progression should be documented in the eCRF but should not be reported as an SAE.
- Death not due (or not clearly due) to progression of the disease under study, the AE causing the death must be reported as an SAE within 24 hours. The SAE form should report the main and contributory causes of death. This information can be captured also in the eCRF.
- Death with an unknown cause should always be reported as an SAE. If the cause of death later becomes available (e.g. after autopsy), the cause of death should be replaced by the established cause of death.

The term “sudden death” should only be used for the occurrence of an abrupt and unexpected death due to presumed cardiac causes in a patient with or without pre-existing heart disease, within 1 hour of the onset of acute symptoms or, in the case of an unwitnessed death, within 24 hours after the patient was last seen alive and stable. If the cause of death later becomes available (e.g. after autopsy), “sudden death” should be replaced by the established cause of death.

### ***Overdose, misuse, abuse, medication errors***

Study drug overdose is the accidental or intentional use of the drug in an amount higher than the dose being studied. An overdose or incorrect administration of study drug (e.g. misuse, abuse, medication errors etc.) is not an AE unless it results in untoward medical effects.

Cases of accidental overdose with ivermectin have been reported, but none have resulted in fatalities. In cases of accidental intoxication with unknown doses of products destined for veterinary use (oral use, as an injection, cutaneous use), the symptoms described were: rash, contact dermatitis, oedema, headache, vertigo, asthenia, nausea, vomiting, diarrhoea and abdominal pain. Other effects have also been observed, including: seizures, ataxia, dyspnoea, paraesthesia and urticaria.

Management in case of accidental intoxication:

- Symptomatic treatment and surveillance in a medical care setting with fluid replacement and hypertensive treatment, if necessary. Although there are no specific

studies available, it is advisable to avoid combination of GABA agonists in the treatment of accidental intoxication due to ivermectin.

Ivermectin must only be used in accordance with the dosing recommendations in this protocol. Any dose or frequency of dosing that exceeds the dosing regimen specified in this protocol should be reported as an overdose.

All AEs associated with an overdose or incorrect administration of study drug should be recorded on the AE form. If the associated AE fulfills seriousness criteria, the event should be reported using SAE form to the Sponsor within 24 h from learning of the event.

### ***Study recording period and follow-up for adverse events and serious adverse events***

Adverse events and serious adverse events will be recorded from time of acquisition of informed consent, throughout the treatment period and including the safety follow-up period (25 days after the last study drug administration). During the course of the study all AEs and SAEs should be proactively followed up for each participant. Every effort should be made to obtain a resolution for all events, even if the events continue after discontinuation/study completion.

The investigator is responsible for following all SAEs until resolution, until the participant returns to baseline status, or until the condition has stabilized with the expectation that it will remain chronic, even if this extends beyond study participation.

### ***Follow-up of unresolved adverse events***

Any AEs that are unresolved up to the end of safety follow up period (25 days after the last study treatment administration) are followed up by the investigator for as long as medically indicated. After 25 days, only subjects with ongoing investigational product-related SAEs will continue to be followed for safety.

### ***Reporting requirements for pregnancies***

National regulations require that clinical trial Sponsors collect information on pregnancies occurring during clinical trials, in which exposure to the study drug at any time during pregnancy, is suspected. Therefore, pregnancy and suspected pregnancy (including a positive pregnancy test) occurring while the patient is on study drug, or within 25 days after the last study drug administration, are considered reportable events.

### ***Maternal exposure***

Pregnancy itself is not regarded as an AE unless there is a suspicion that the study drugs may have interfered with the effectiveness of a contraceptive medication. Any pregnancy, suspected pregnancy, or positive pregnancy test must be reported to the Study safety desk immediately and always within 24 hours from its first knowledge.

Immediately after detecting a case of suspected pregnancy in a clinical trial patient, a decision to continue the pregnancy will require immediate withdrawal from the trial.

The Investigator will follow the pregnancy until its outcome, and must notify the Study safety desk the outcome of the pregnancy as a follow-up to the initial report. For any event during the pregnancy, which meets a seriousness criterion, the Investigator will also follow the procedures for reporting SAEs (complete and send the SAE form to the study safety desk within 24 hours of the Investigator's knowledge of the event). All spontaneous miscarriages, congenital abnormalities or birth defects and neonatal deaths that occur within 30 days from birth without regard to causality and any infant death that the Investigator suspects to be related to exposure to the study drug should be immediately reported and always within 24 hours from the Investigators' knowledge of the event as SAE. The outcome of all pregnancies should be followed up and documented even if the patient was discontinued from the study.

## **PHARMACOKINETICS STUDY**

A pharmacokinetics study aimed at evaluating the association between plasma drug concentration and clinical endpoints is planned.

The study will be conducted on a subgroup of patients, according to the details in Appendix 1.

For patients included in the study an additional informed consent will be required.

## **ETHICAL ASPECTS**

This study is to be conducted according to globally accepted standards of good clinical practice (as defined in the ICH E6 Guideline for Good Clinical Practice, 1 May 1996), in agreement with the Declaration of Helsinki and in keeping with local regulations.

Written approval of the protocol and the associated study documentation will be obtained from the Competent Ethics Committees and from the National regulatory authority, according to local regulations.

Approval letters must contain the following information:

- Date of the meeting
- Information that identifies the version of both the protocol and the subject information/informed consent
- Details of any other documents reviewed

All protocol amendments will be submitted to the Ethics Committees for approval prior to implementation, except for any urgent amendments to ensure patient safety, which will be immediately implemented and then notified as soon as possible to the Ethics Committees and competent Authorities. In addition the Ethics Committees will be informed of any administrative changes.

Raw anonymized data sets will be available to the scientific community upon legitimate request, once the trial is completed.

### ***Informed consent***

It is an Investigator responsibility to inform and obtain the patient Informed Consent. In accordance with the AIFA communication «*Clinical trials' management in Italy during the COVID-19 (coronavirus disease 19) emergency (March 12th 2020)* », eligible patients will be directly asked (if still present at hospital at the moment of the positive test result) or by phone interview (if at home) their consent for study entry. For patients directly enrolled at hospital or other study site by the investigator, informed consent will be collected orally and certified by the investigator himself and by a witness, given the impossibility of keeping potentially infected material. Patients enrolled at home, after an initial telephone conversation, will receive the information and consent forms by email and send them back signed in digital format (pdf scan). In both cases, the patient will be asked to re-sign the original consents for the conservation in the trial master file at the first useful occasion after the sample has become negative.

The Informed consent procedure will be in accordance with the European Regulation n. 679/2016 on the Protection of Personal Data, the Personal Data Protection Code (Legislative Decree 196/03) and subsequent amendments and additions, and to the provisions, guidelines and general authorizations of the National Guarantor for Personal Data Protection.

### ***Participant confidentiality***

The Sponsor maintains confidentiality standards by coding each patient enrolled in the study through assignment of a unique patient identification number.

This means that patient names are not included in data sets that are transmitted to any Sponsor location.

Patient medical information obtained by this study is confidential and may only be disclosed to third parties as permitted by the ICF (or separate authorization for use and disclosure of personal health information) signed by the patient, unless permitted or required by law.

Medical information may be given to a patient's personal physician or other appropriate medical personnel responsible for the patient's welfare, for treatment purposes.

Data generated by this study must be available for inspection upon request by representatives of the national and local health authorities, Sponsor monitors, representatives, and collaborators, and the IEC for each study site, as appropriate.

### ***Data handling and record keeping***

Records and documents pertaining to the conduct of this study, including eCRFs, ICFs, Investigator Site Files (ISFs) must be retained by the Principal Investigator for at least 15 years after completion or discontinuation of the study, or for the length of time required by relevant national or local health authorities, whichever is longer. After that period of time, the documents may be destroyed, participant to local regulations.

No records may be disposed without the written approval of the Sponsor.

Written notification should be provided to the Sponsor prior to transferring any records to another party or moving them to another location.

## **DATA MANAGEMENT**

### ***Source Data***

Source documents are where data is first recorded, and from which participants' eCRF data are obtained. These include, but are not limited to, hospital records (from which medical history and previous and concurrent medication may be summarised into the eCRF), clinical and office charts, laboratory and pharmacy records, diaries, microfiches, radiographs, and correspondence.

eCRF entries will be considered source data if the CRF is the site of the original recording (e.g. there is no other written or electronic record of data). All documents will be stored safely in confidential conditions.

On all trial-specific documents, other than the signed consent, the participant will be referred to by the trial participant number/code.

### ***Collection of Data, Direct Entry***

All data obtained during this clinical trial will be captured electronically in a project specific programmed EDC application. The eCRFs were specifically designed for the collection of the clinical data detailed in this trial protocol.

All data entered into the eCRF will have to be verified by the original patient's file.

For each patient enrolled after allocation of a Patient ID, all trial-related visits will be recorded in the eCRF. This eCRF must be completed by the Investigator for all patients, whether they completed the trial according to protocol or dropped out prematurely.

In particular, a web-based Clinical Data Management System (CDMS/eCRF) supported by REDCap, a secure web platform for building and managing online databases and surveys (<https://redcap.marionegri.it/>) will be used for collecting information for all patients. Each user has their own account, and their user account will only have access to REDCap projects which other users have granted them access. eCRF administrator will organize users in different roles groups. There are user controls to limit access to various functionality and modules, such as being able to export data, to enter data, to add or modify database fields or survey questions, to build or run reports, to modify user privileges, to view the logging records, and so on.

## **Monitoring**

Due to pandemic situation and in accordance with the AIFA communication «*Clinical trials' management in Italy during the COVID-19 (coronavirus disease 19) emergency (March 12th 2020)* », the monitoring activities will be performed remotely. Remote monitoring visit will be performed through periodic, comprehensive connections through the web or the telephone with all participating centres by Sponsor personnel or representatives in order to perform, if applicable, the source data verification (SDV).

More details of the monitoring procedures will be specified in the Monitoring Plan.

In accordance with applicable regulations including Good Clinical Practice (GCP), monitors will contact the sites prior to the start of the study to review with the site staff the protocol, study requirements, and their responsibilities to satisfy regulatory and ethical requirements. When reviewing data collection procedures, the discussion will also include identification, agreement and documentation of the source document for all data items.

Site activities will be monitored to verify that:

- Data are authentic, accurate and complete
- Safety and rights of subjects are being protected
- Study is conducted in accordance with the currently approved protocol and any other study agreements, GCP, and all applicable regulatory requirements.

## **PROCEDURE FOR THE CONCLUSION OF THE TRIAL**

The trial will be concluded when the expected number of patients to be enrolled will be reached, or before if unexpectedly serious/frequent adverse events should be recorded in one or in both the treatment groups. In case this only happens in the arm b) of the treatment group, this arm will be immediately stopped and the trial will continue with the comparator group and the arm a) of the treatment group.

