## **STUDY DESIGN**

This is a multicentre, prospective, randomized, double-blind, adaptive phase II dose finding study.

Patients meeting the inclusion criteria will be asked to participate to the study and randomized in a 1:1:1 ratio to either:

- Placebo arm (arm A): placebo will be identical in appearance to ivermectin in order to preserve blinding and will be administered p.o. at empty stomach with water once daily, for 5 days

- Intervention arms: a) Ivermectin, single dose 600 µg/kg, for 5 days (I\_600) and placebo (arm B) ; b) Ivermectin, single dose 1200 µg/kg, for 5 days (I\_1200) (arm C) ); these drugs will be administered p.o. once daily, for 5 days.

In arm A and B, the number of placebo tablets to be administered will be calculated by the study dedicated pharmacist considering the number of tablets that should be taken in case a patient with the same weight is assigned to arm C.

[figure not shown]
Patients will be randomized by a centralized computer system. At randomization a treatment ID is assigned to the patient. Once a treatment ID is assigned this must not be re-assigned even in cases of errors.

Enrolled subjects will be identified by a unique subject number (patient code) that will remain consistent for the duration of the study.

Patients will be recruited at the emergency room of hospitals, and/or among asymptomatic hospital workers found positive for SARS-CoV-2 at routine screening and/or in outpatient ambulatory settings, and/or at home, if not meeting the clinical criteria for hospitalization, according to the routine procedure of each participating site. The expected duration of subjects inclusion in the study is of 3 months, or until the planned number of subjects to be enrolled will be reached.

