### ***Primary outcomes***

1. Number of serious adverse drug reaction (SADR).
2. Quantitative viral load at Day 7 as measured by quantitative, digital droplet PCR.

NB: The primary outcome no.2., as well as all secondary outcomes, will be measured only if the number of SADR is less than 4 in at least one of the treatment arms.

---

 1 is "no limitation of activities", 2 is "limitation of activities", 3 is "hospitalized, no oxygen therapy", 4 is "hospitalized, oxygen by mask or nasal prongs", 5 is "non-invasive ventilation or high-flow oxygen", 6 is "intubation and mechanical ventilation", 7 is "ventilation + additional organ support - pressors, RRT (renal replacement therapy), ECMO (extracorporeal membrane oxygenation)", and 8 is "death".

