### **Step 1:**

#### Safety analysis

After randomisation of the first 60 evaluable patients (20 per arm) a first analysis will be performed on the 2 experimental treatments for safety purpose. Safety endpoint will be the occurrence of a SADR. Definitions are reported in the paragraph «Definition and reporting of adverse events»

A'Hern single stage design (A'Hern 2001) will be adopted. For each experimental arm, the null hypothesis that the true toxicity rate is 30% will be tested against a one-sided alternative. The null hypothesis will be rejected if  $\leq 4$  SADRs are observed in 20 patients. This design yields a type I error rate of 10% and power of 80% when the true toxicity rate is 5%.

If  $\geq 5$  SADRs are observed in one of the experimental arms, the allocation of patients to that arm will be interrupted and the study will continue for efficacy analysis only for the control arm and the other treatment arm. In case that  $\geq 5$  SADRs will be experienced in both arms the study will be stopped.

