### ***End of Study***

The end of the study is defined as the last follow-up visit of the last patient. The Ethics Committees will be notified within 90 days of the end of the study.

Recruitment will be stopped once the required number of patients is reached or in case of (unexpected and most unlikely) severe adverse events in the treatment arm or if the analysis of the first step will show an unfavorable safety profile of both experimental arms.

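### The Step 1 safety rule (pass at 4 or fewer SADRs in 20) has a type I error of 23.8%, not the stated 10%, and disagrees with the gate of fewer than 4 in Primary outcomes

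*Protocol*

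**What the plan says.** The Safety analysis under Step 1 (protocol, Statistical design and sample size) applies an A'Hern single-stage design to each experimental arm, with 20 evaluable patients per arm. The null hypothesis is a toxicity rate of 30%. It is rejected, and the arm is treated as safe, when 4 or fewer SADRs are seen. The section then claims: "This design yields a type I error rate of 10% and power of 80% when the true toxicity rate is 5" per cent. If one experimental arm has 5 or more SADRs, "the allocation of patients to that arm will be interrupted and the study will continue for efficacy analysis only for the control arm", together with the remaining dose. If both have 5 or more, the study stops.

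The note under Primary outcomes says that the viral load outcome and all secondary outcomes "will be measured only if the number of SADR is less than 4 in at least one of the treatment arms".

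Two later sections also deal with stopping for safety:

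- End of Study has two safety triggers for stopping recruitment. One is a matter of judgement: "in case of (unexpected and most unlikely) severe adverse events in the treatment arm". The other depends on the Step 1 result: "if the analysis of the first step will show an unfavorable safety profile of both experimental arms".
- Procedure for the Conclusion of the Trial ends the trial at full enrolment, "or before if unexpectedly serious/frequent adverse events should be recorded in one or in both the treatment groups". It makes one exception: "In case this only happens in the arm b) of the treatment group, this arm will be immediately stopped". The comparator and arm a) then carry on.

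Study Design gives the lower-case labels: a) is 600 µg/kg "and placebo (arm B) ; b) Ivermectin, single dose 1200" µg/kg.

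**The concern.** Step 1 decides whether an arm given five daily doses at 3 or 6 times the usual single antiparasitic dose (200 µg/kg, according to the Introduction) goes on to more patients. Two things about it look wrong.

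First, a cut-off of 4 in 20 looks too lenient for a 10% chance of passing an arm whose true SADR rate is 30%. If so, ethics committees and investigators have been given too favourable a figure for the risk of carrying an unsafe dose forward.

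Second, Primary outcomes and Step 1 use different numbers for what reads as the same decision. A count of 4 satisfies at most 4 but not fewer than 4. For some results the protocol would both require and forbid the efficacy analysis.

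A smaller question is whether the section on concluding the trial handles toxicity in one arm as Step 1 does.

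**Working it through.** **Inputs.** From Step 1: n = 20 per arm, null rate 30%, acceptable rate 5%, pass at ≤4, stop at ≥5, stated type I error 10% and power 80%. From Primary outcomes: fewer than 4 SADRs in at least one treatment arm. Rates of 10% and 20% are used below as assumptions only. X is the number of patients with a SADR in an arm, X ~ Bin(20, p), and the arms are taken as independent.

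**1. The plan's own figure.** Type I error is P(X ≤ 4 | p = 0.30), the sum over k = 0 to 4 of C(20,k) × 0.3^k × 0.7^(20−k):

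0.0008 + 0.0068 + 0.0278 + 0.0716 + 0.1304 = 0.2375 (from unrounded terms).

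Power is P(X ≤ 4 | p = 0.05) = 0.9974. The stated 10% and 80% are not reproduced. The neighbouring cut-offs are:

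| Pass if | Type I error (30%) | Power (5%) | P(pass) at 10% |
|---|---|---|---|
| ≤2 | 0.0355 | 0.9245 | 0.6769 |
| ≤3 | 0.1071 | 0.9841 | 0.8670 |
| ≤4 (Step 1) | 0.2375 | 0.9974 | 0.9568 |
| ≤5 | 0.4164 | 0.9997 | 0.9887 |

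If 80% is read as a minimum, the first three rows all meet it. If 10% is read as a maximum, only ≤2 meets it. The cut-off closest to 10% is ≤3, which is also the one implied by fewer than 4 in Primary outcomes.

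**2. When the two sections disagree.** Step 1 goes on to efficacy unless both arms have ≥5. Primary outcomes measures efficacy unless both arms have ≥4. They give opposite answers when both arms have ≥4 but not both have ≥5, that is, when the lower count is exactly 4:

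P = P(X ≥ 4)² − P(X ≥ 5)², with the same rate in both arms.

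- 5%: 0.0159² − 0.0026² = 0.0002
- 10% (assumed): 0.1330² − 0.0432² = 0.016
- 20% (assumed): 0.5886² − 0.3704² = 0.209
- 30%: 0.8929² − 0.7625² = 0.216

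**3. What both sections do together if applied literally.** An arm with a 30% rate is compared for efficacy if it has ≤3, or if it has exactly 4 and the other arm has ≤3:

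P = 0.1071 + 0.1304 × P(other arm ≤ 3).

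With the other arm at 5%, 10%, 20% or 30%, P(other arm ≤ 3) is 0.9841, 0.8670, 0.4114 or 0.1071. The result is 0.235, 0.220, 0.161 or 0.121.

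**4. Toxicity in the 600 µg/kg arm alone.** Under Step 1, an arm B count of ≥5 with arm C at ≤4 stops B and continues C against placebo. The section on concluding the trial names one or both groups in its general rule and exempts only b), which is 1200 µg/kg. The 600-only case therefore falls under the general rule. The chance of that SADR pattern is P(X₆₀₀ ≥ 5) × P(X₁₂₀₀ ≤ 4):

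- 5%/5%: 0.0026 × 0.9974 = 0.003
- 10%/20% (assumed): 0.0432 × 0.6296 = 0.027
- 20%/30% (20% assumed): 0.3704 × 0.2375 = 0.088

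A conflict also requires the same events to meet that section's unquantified trigger.

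**The case against.** **The Primary outcomes gate is not a per-arm rule.** This stands. It asks for fewer than 4 in at least one arm. If one arm has 4 and the other has 3 or fewer, the gate is open, Step 1 passes both arms, and nothing conflicts. A reader might infer that the choice between the two sections moves the chance of passing a 30% arm from 23.8% to 10.7%. The text does not support that: step 3 of the working gives 0.12 to 0.24. The 10.7% belongs to a per-arm cut-off of 3, which is the remedy proposed here and not what the protocol now says.

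**The gate gives no denominator and does not mention Step 1.** True, so tying it to 20 patients per arm is an inference. It is a reasonable one, because Step 1 is the only place where SADRs decide whether efficacy is pursued.

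**At acceptable toxicity the clash almost never occurs.** Also true: 0.02% at 5%. A safety rule is judged at rates where it might have to act, however, and 30% is the protocol's own null. The misstated type I error does not depend on the clash at all.

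**The section on concluding the trial is a separate safeguard.** Much of this stands. Its trigger is a judgement about adverse events with no fixed time; Step 1 is a SADR count at a planned look. A reader might infer that the protocol flatly orders the trial to end if only 600 µg/kg is toxic. It does not say so. That outcome follows from a general rule plus one exception, and the Step 1 clause in End of Study agrees with Step 1 in requiring both arms. The asymmetry may also be intended, since few would continue 1200 µg/kg after 600 µg/kg proved toxic. What remains is narrow: where both triggers are met the actions differ, and nothing says which prevails. Reading b) as capital Arm B does not help, because a) would then be placebo, which the same sentence lists separately as the comparator.

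**Conclusion.** The main point holds. The cut-off in Step 1 does not have the operating characteristics stated beside it: the type I error is 23.8% against 10%, and the power is 99.7% against 80%. These are exact binomial results from the protocol's own inputs, treating each SADR as one affected patient.

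Primary outcomes contradicts Step 1 when the lower arm count is exactly 4. With independent arms and equal rates, that has a probability of 0.02% at 5% and 21.6% at 30%. The disagreement concerns whether efficacy is assessed at all. It is not a second per-arm error rate.

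The mismatch in the section on concluding the trial is minor. It is confined to events that meet both triggers and changes no error rate. Whether toxicity at 600 µg/kg should also stop 1200 µg/kg is a clinical choice that this review does not settle.

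**What to change.** Use one per-arm cut-off in both Step 1 and Primary outcomes: pass an arm at 3 or fewer SADRs in 20 and stop it at 4 or more. Restate the operating characteristics as type I error 0.107 at 30% and power 0.984 at 5%. There are two alternatives:

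- If 10% is a hard limit, pass at 2 or fewer (0.035 and 0.925).
- If 4 or fewer is kept, state its type I error as 0.238 and its power as 0.997, and change the gate in Primary outcomes to match.

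In the section on concluding the trial, use the A/B/C labels and either refer to the Step 1 rule or say that this is a judgemental stop that overrides it. The sponsor and clinicians should decide whether toxicity in arm B also stops arm C; if it does, Step 1 should say so.

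The cost is protocol wording, with no extra patients or procedures. The price of 3 against 4 is that a safe arm is dropped more often: 1.6% against 0.3% at a 5% rate, and 13.3% against 4.3% at an assumed 10%. A cut-off of 2 costs more: 1 − 0.9245 = 7.6% at 5% and 1 − 0.6769 = 32.3% at 10%.
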